Prior data demonstrates that a single oral dose of inorganic nitrate reduces late systolic load in other populations. Dietary nitrate increases plasma nitrite, an endothelium-independent source of the potent vasodilator nitric oxide (NO). Thus, augmentation of the nitrate-nitrite-NO pathway has the potential for chronic "disease-modifying" benefits in aortic stenosis. Therefore, nitrate supplementation represents a logical intervention to improve exercise capacity and quality of life in aortic stenosis.

The current trial is designed to assess the safety and efficacy of sustained oral administration of inorganic nitrate in patients with severe aortic stenosis and to assess the mechanisms by which inorganic nitrate enhances oxygen uptake and exercise capacity in this population. This is a randomized double-blind crossover clinical trial, in which 22 subjects who underwent surgical or transcatheter AVR for severe AS three or more months prior to enrollment will receive the following 2 interventions, in randomized order: (1) Potassium nitrate (KNO₃), at a dose of 12-18 mmol/d by mouth for 4 ± 1 weeks, or; (2) Potassium chloride (KCI), at a dose of 12-18 mmol/d by mouth for 4 ± 1 weeks. A 1-week ± 3 day washout period will be introduced between the 2 interventions. The purpose of the trial is to test the safety of KNO₃ and its efficacy on a number of clinical and physiologic endpoints in subjects who underwent AVR for severe AS.

Our specific aims are:

Specific Aim 1: To assess whether KNO_3 therapy improves endpoints with direct clinical relevance: aerobic capacity and quality of life (QOL)

Hypothesis 1a: KNO_3 will improve exercise capacity, quantified as: (1) Total work performed during a maximal-effort exercise test; (2) Peak oxygen consumption (VO₂) during a symptom-limited maximal effort exercise test. These will be the co-primary endpoints of the trial.

Hypothesis 1b: KNO_3 will improve QOL, assessed using the Kansas City Cardiomyopathy Questionnaire.

Specific Aim 2: To dissect the effects of KNO₃ on specific physiologic adaptations to exercise

Hypothesis 2a: KNO_3 improves the systemic vasodilator response to exercise, measured as the change in systemic vascular resistance during a symptom-limited maximal effort exercise test.

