2. TRIAL SUMMARY TABLE (OBJECTIVES AND ENDPOINTS)

Trial Title / Acronym	Targeting Pu lsatile Load to Increa s e E xercise Capacity and Quality of Life After Aortic Valve Repair for Severe A ortic S tenosis (PULSE AS)					
Phase	Phase IIb Randomized Clinical Trial (RCT)					
Number of Subjects	22					
Patient Population	Ages 50-90; 3 or more months after AVR for severe AS					
Study Site	University of Pennsylvania					
Study Design	Randomized, double-blinded crossover study					
Randomized Intervention	Potassium Nitrate (KNO ₃) capsules, at a dose of 6 mEq (1 capsule) three times daily for 4 ± 1 weeks, versus, potassium chloride (KCI) capsules administered at a dose of 6 mEq (1 capsule) three times daily for 4 ± 1 weeks					
Primary Aim	To assess whether KNO_3 therapy improves exercise capacity, quantifier as: (1) Total work performed during a maximal-effort exercise test; and (2) Peak oxygen consumption (VO ₂) during a symptom-limited maximal effort exercise test. These will be the co-primary endpoints of the trial.					
Secondary Aims	 To assess whether KNO_{3:} improves quality of life improves the systemic vasodilator response to exercise improves LV diastolic function and myocardial systolic strain reduces late systolic LV load from wave reflections 					
Exploratory Aims	To assess whether KNO ₃ improves:					
	 Ventilatory threshold, VO₂ kinetics Natriuretic peptide levels Physical activity 					
	To assess the relationship between nitrate and nitrite levels achieved and the therapeutic response achieved in each subject (e.g., improvement in endpoints in response to KNO ₃ vs control). To assess the effect on RNA expression.					
Primary Endpoints	Peak oxygen uptake (VO₂) during a symptom-limited maximal effort exercise test after 4 ± 1 weeks of KNO ₃ vs KCI					
	Quality of life score , assessed using the Kansas City Cardiomyopathy Questionnaire					
Secondary Endpoints	Measures of LV diastolic function (E/e', left atrial volume index),and peak global systolic myocardial longitudinal and circumferential strain					
	Augmentation index, late systolic wall stress and aortic input impedance					

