8. STUDY MEASUREMENTS AND DATA COLLECTION

8.1. Assessment of exercise capacity

We will use a supine bicycle exercise protocol in conjunction with expired gas analysis to assess oxygen consumption (VO₂) during exercise. Subjects will perform a maximal exertion-limited exercise test using a graded-exercise protocol. We will use a supine cycle ergometer designed for stress echocardiography (Stress Echo Ergometer 1505, Medical Positioning, Inc, Kansas City, MO). Subjects will undergo expired gas analysis with a Parvo Medics True One 2400 device (Parvo Medics, Sandy, UT), an Innocor device (Innovision Inc) or equivalent. Resistance began at 15 W for 3 minutes, increasing to 25 W for 3 minutes, and then increasing by 25 W every 3 minutes thereafter. Breath-by-breath information will be recorded. We will use custom-designed software already developed in Matlab (MathWorks, Natick, MA) at our lab for offline processing and quantification of all exercise data.⁽⁸⁵⁾ All data quantification will be blinded to treatment. Total work performed will be computed and exercise efficiency will be defined as (total work/total oxygen consumed). Exercise efficiency is not a formal endpoint of the trial, but will be used to interpret changes in the co-primary outcomes. After these exercises, we will use a device that uses Near Infrared Spectroscopy [NIRS] to measure the oxygen levels in the left calf and forearm muscles (Portamon and Portalite devices, Artemis, Netherlands).

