10. STATISTICAL CONSIDERATIONS

10.1. Power calculations

We will randomize 22 subjects to one of 2 sequences (i), each of which consists of 2 periods (AB/BA design). We now have pilot data regarding the distribution of the changes in peak VO₂ (the primary endpoint of the study) as well as various secondary endpoints, among patients with HFpEF. We considered an increase in peak VO₂ of ~0.6 ml/kg/min to be the minimum clinically-significant change. This was based on the fact that even "modest" changes of comparable magnitude in peak VO₂ have been associated with improved outcomes.⁽¹¹⁰⁾ The standard deviation of the change in peak VO₂ in our pilot trial was 1.23 ml/kg/min. Therefore, the standardized effect size is 0.49 or greater. Assuming a 90% retention rate, enrolling 22 subjects in this cross-over trial will have 80% power to detect an effect size as low as 0.66 in the intervention-induced change of our study endpoints, with a two-sided α =0.05.

Based on the distribution of the changes in study endpoints from repeated measurements of the Kansas City Cardiomyopathy Questionnaire in AS patients, we estimated that this trial study is powered (80%) to detect the following changes in other endpoints: 4.6 points for the Kansas City Cardiomyopathy Questionnaire, 8.2% for exercise vasodilatory reserve, 19% for cardiac output reserve and 4.2% change in reflection magnitude. We note that these differences are well below what is considered a clinically significant change in KCCQ (10 points or more, http://cvoutcomes.org/pages/3217) or the effect size that has been observed for these endpoints in our pilot trial.⁽⁸⁵⁾ Therefore, we are confident that we will achieve adequate power not only for our clinical endpoints, but also for our physiologic measures. PASS11⁽¹¹¹⁾ was used to perform power analyses.

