10.2. Data Analysis Plan

The co-primary outcome variables will be peak VO_2 and KCCQ score. All secondary outcome measures are continuous variables. The predictor of interest for all aims will be intervention (KNO₃ therapy vs. control), with analyses based upon the total number of subjects randomized. Initial descriptive estimates of all measures will be generated for study participants at each time point by treatment group. Statistics will include estimates of central tendency, measures of variability, and derived moments of skewness and kurtosis. Analyses of distributional properties will be performed to determine if variance stabilizing or normalizing transformations should be applied. Outliers will be assessed via visual inspection of distributions and checked for accuracy. Aim 1 will assess the effects of potassium nitrate therapy on peak O2 / work performed and quality of life score (co-primary outcomes). An initial assessment of the treatment effect will be performed using the paired t-test and the non-parametric Wilcoxon sign-rank test on the difference between the paired within subject outcome measures. This will be followed by a more comprehensive linear mixed-effects model analysis⁽¹¹²⁾ allowing for assessments of the treatment effect on each continuous outcome of interest while controlling for effects of other covariates such as period, sequence, and a random subject effect nested within sequence. For non-normal distributed outcomes, we will utilize non-parametric methods or consider distribution-stabilizing transformations. The intervention groups will initially be compared within each period (time invariant covariates will only be compared for period 1) according to continuous covariates

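### Peak VO2 is primary throughout, but the documents disagree on what else is primary (total work, KCCQ or nothing) and give no rule for judging success across endpoints

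*Combined protocol and SAP*

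**What the plan says.** Section 1 (Hypothesis 1a) defines exercise capacity by two measures, "1) Total work performed during a maximal-effort exercise test; (2) Peak oxygen consumption (VO₂) during a symptom-limited maximal effort exercise test", and adds: "These will be the co-primary endpoints of the trial". Quality of life is a separate Hypothesis 1b, that treatment "will improve QOL, assessed using the Kansas City Cardiomyopathy Questionnaire".

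Section 2, Primary Aim row, repeats the pair: "1) Total work performed during a maximal-effort exercise test; and (2) Peak oxygen consumption". The Secondary Aims row includes the aim that treatment "improves quality of life".

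Section 8.1 says: "Exercise efficiency is not a formal endpoint of the trial, but will be used to interpret changes in the co-primary outcomes". It names no outcomes there. But efficiency is work divided by oxygen consumed, so the sentence fits the pair of total work and peak VO2.

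Section 10.1 refers to "changes in peak VO₂ (the primary endpoint of the study" and lists KCCQ among the other endpoints. It gives one two-sided alpha of 0.05, and no effect, SD or detectable difference for total work.

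Section 10.2 opens its endpoint definition with "The co-primary outcome variables will be peak VO_2 and KCCQ score". A later sentence of the same section lists peak oxygen uptake, work performed and the quality-of-life score together as co-primary, which could mean two or three measures. It then plans separate models for two outcome measures without naming them.

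**The concern.** The primary endpoint set decides what the trial can claim. Here the current text supports three sets: peak VO2 with total work, peak VO2 with KCCQ, and peak VO2 alone. A fourth, with all three measures, is arguable. Someone who has seen the results could promote or demote total work or KCCQ and cite the protocol either way.

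The missing decision rule adds to this. With two primary endpoints, either-suffices and both-required carry different error rates and different power. The power statement in Section 10.1 is tied to neither.

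**Working it through.** **Definitions side by side**

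| Place | Peak VO2 | Total work | KCCQ |
|---|---|---|---|
| Section 1 | co-primary | co-primary | separate hypothesis |
| Section 2, Primary and Secondary Aim rows | co-primary | co-primary | secondary |
| Section 10.1 | the primary endpoint | no figures given | among other endpoints |
| Section 10.2, first sentence | co-primary | not named | co-primary |
| Section 10.2, later sentence | co-primary | apparently co-primary | co-primary |

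Only peak VO2 is constant.

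**Inputs (Section 10.1).** 22 enrolled, 90% retention, two-sided alpha 0.05, 80% power at 0.66 SD. For peak VO2, a minimum important change of 0.6 ml/kg/min and SD 1.23. For KCCQ, a detectable change of 4.6 points and a clinically significant change of 10 points. Completers: 22 × 0.90 = 19.8, taken as 20. Correlation between endpoints is not given, so 0 to 0.9 is assumed.

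**1. Reproduce the stated power.** Paired t-test, noncentral t with ncp = d√n and df = n − 1. At d = 0.66, n = 20 and alpha 0.05, power is 79.9%. The stated figure is that of one unadjusted test. At alpha 0.025, power is 69.6%.

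**2. If either of two suffices, each at 0.05.** With independent endpoints, family-wise error = 1 − 0.95² = 9.75%. Simulated correlated t statistics give about 8.4% at correlation 0.7 and about 7% at 0.9. For three independent endpoints, 1 − 0.95³ = 14.3%.

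**3. If both are required, each at 0.05.** Type I error is controlled, and power depends on both effects.
- 0.66 SD on both: 0.799² = 64% (correlation 0), 71% (0.7), 75% (0.9).
- Very large second effect: the SD implied for KCCQ is 4.6/0.66 = 6.97, so 10 points is 10/6.97 = 1.43 SD. Power for that test is essentially 100%, and joint power is about 80% at every correlation.

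**4. Peak VO2 alone at the plan's own minimum effect.** 0.6/1.23 = 0.49 SD. Power with 20 completers is 54%.

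**5. Holm over two endpoints.** The smaller p-value is tested at 0.025, then the other at 0.05. Simulated power for peak VO2, correlation 0 to 0.9:

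| Peak VO2 effect | Other effect | Power under Holm | Alone at 0.05 |
|---|---|---|---|
| 0.66 SD | 1.43 SD | 80% | 80% |
| 0.66 SD | 0.66 SD | 74% to 77% | 80% |
| 0.66 SD | 0.49 SD | 70% to 74% | 80% |
| 0.66 SD | 0.3 SD or less | about 70% | 80% |
| 0.49 SD | 0.49 SD | about 46% to 47% | 54% |

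**The case against.** The strongest reply is that co-primary conventionally means that all endpoints must succeed, so no alpha adjustment is needed. The documents never define the word that way. That reading would also leave the pair unsettled, and the 80% in Section 10.1 would then not be the power of the success criterion.

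A second reply is that Section 10.1 settles the matter as peak VO2 alone. It may be shorthand. Sections 1, 2, 8.1 and 10.2 all speak of co-primary endpoints or outcomes, and Sections 1 and 10.2 conflict without it.

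Some stronger readings are tempting but unsupported:
- **That the trial runs at nearly 10% type I error.** This needs an either-suffices rule, which no section states. The and/or wording in Section 11.1 describes possible benefit and is not a test rule.
- **That requiring both endpoints always costs power.** With a second effect of 1.43 SD there is essentially no loss.
- **That 9.75% and 64% are expected values.** They assume zero correlation, which is least plausible for total work and peak VO2, since both come from the same exercise test.
- **That the Primary Endpoints row of Section 2 confirms KCCQ as primary.** The row boundary is uncertain in the extracted table, so it is given no weight.

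**Conclusion.** The contradiction and the missing success rule are firm. They rest on complete sentences in the current text and on no numerical assumption. They should be resolved before unblinding, because a choice made afterwards would not be credible.

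The size of the consequence is conditional. It depends on the rule eventually chosen, on 20 completers, on an assumed correlation of 0 to 0.9, and on the second effect. The 1.43 SD case further assumes that the KCCQ detectable change was computed at 0.66 SD. What can be said without choosing a rule is that the stated 80% describes a single endpoint tested at 0.05.

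**What to change.** Before unblinding, write one identical primary definition, with its decision rule, into Sections 1, 2, 8.1, 10.1 and 10.2. Either option removes the contradiction.

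**(a) Preferred: peak VO2 as the single primary endpoint at two-sided 0.05.** It is the only endpoint common to all versions and the only one with both a stated effect and a stated SD. Total work and KCCQ become key secondaries in a fixed sequence, in an order that the sponsor sets in advance. Each is tested at 0.05 only if the preceding test is significant. Cost: at 0.49 SD peak VO2 is significant in only about 54% of trials, so the secondaries would go formally untested in about 46%.

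**(b) Keep two co-primaries.** Name the pair. State either that both are required, each at 0.05, or that either suffices with Holm. Restate power for that rule, and add an assumed effect and SD for total work if it is in the pair. Cost if both are required: the joint power in step 3. Cost under Holm: up to about 10 percentage points for peak VO2 at 0.66 SD. A fall to about 70% does not need a null second endpoint, since a second effect of 0.3 SD already produces it. At 0.49 SD on both, the loss is 7 to 8 points.

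Neither option needs new data or visits. The work is protocol and SAP wording and, under (b), a restated power figure.

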Hypotheses 2b: Since nitrates may exert venodilating effects and/or myocardial effects, we will test the hypotheses that KNO₃ impacts LV diastolic filling parameters (measured with echocardiography at rest and after peak exercise) and improves myocardial strain (assessed with speckle-tracking echocardiography).

Specific Aim 3: To assess whether KNO₃ reduces late systolic LV load from wave reflections (assessed via comprehensive aortic pressure-flow relations, using arterial tonometry and Doppler echocardiography).

This trial has the potential to establish a novel, inexpensive, and readily implementable therapeutic paradigm for post-AVR patients and to characterize specific mechanisms involved, enhancing our understanding of this disease.

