- 3. New treatment with organic nitrates or phosphodiesterase inhibitors that cannot be withheld.

- 4. Serum K>5.5 mEq/L.
- 5. Any medical condition that, in the opinion of the investigator, will interfere with the safe completion of the study, or the validity of endpoint assessments. These ad-hoc discontinuations will be discussed with the PI of the trial and the medical director of the IND.

In the following situations, subjects who meet the criteria below will not be immediately discontinued, but will be scheduled for an ad hoc visit for reassessment of values prior to drug initiation in phase 2:

- 1. Supine systolic blood pressure < 90 mm Hg
- 2. Acute kidney injury with eGFR < 30 mL/min/1.73m2
- 3. Methemoglobinemia baseline methemoglobin level > 5%

If these criteria persist during the ad-hoc visit, the subject will be discontinued from the study.

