5.4. Washout period

Following the endpoint assessment, subjects will enter a 1-week \pm 3 day washout period during which they will not receive any study medications.

At 3 weeks into each interventional phase, the Actigraph device will be mailed to the subjects. The goal will be for the subjects to wear this devices on their wrist during the final week of each interventional phase to look for differences with each therapy. The device will be returned by the subject at the endpoint assessment.

5.5. Intervention Phase 2

Following the washout period, subjects will receive either active drug (KNO₃) or control (KCI) during phase 2 of the trial. Subjects will receive the intervention (KNO₃ or KCI) that was not administered to them in phase 1, such that each subject will receive both study interventions in this cross-over design. The ~1-week call and the ~4-week study visit will be repeated as above. We will provide subjects with a 14-day supply of study medication to account for potential delays in receipt of the 2nd batch of medication (i.e., after the 1-week call).

1-week call: Subjects will be called by telephone ~1 week later to assess if they are experiencingside-effects. Subjects will receive reinforcement of the dietary restrictions imposed during the study. Subjects will be asked about headaches and dizziness. If these symptoms are not present, or are not different than the subject's baseline, the drug dose will be up-titrated to 18 mmol daily (One 6-mmol capsule taken 3 times per day). The presence of orthostatic symptoms will prompt a visit to assess for orthostatic vital signs. The presence of symptomatic orthostatic hypotension (20 mmHg reduction in systolic blood pressure with associated symptoms such as dizziness) at the follow up visit will prompt exclusion of patients from the trial.

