described above using parametric or non-parametric one-way ANOVA models, depending upon whether or not normality appears to be in question. Levine's tests will be used to assess homogeneity of variance. Additionally, the intervention groups will be compared within period according to categorical covariates using Fisher's Exact tests. Significant differences between groups on these variables will result in their use as control variables in the modeling of outcome. Separate models will be generated for each of the two outcome measures, with each outcome measure regressed on intervention group assignment, along with baseline outcome and any other covariates deemed prognostic in preliminary analyses. The linear mixed-effects models will incorporate adjustments for any period effect and include data from dropouts.⁽¹¹³⁻¹¹⁵⁾ The model will include subject-specific intercepts as random effects, and assumes independent and identically distributed random errors within subject. Restricted maximum likelihood estimation will be used, and an appropriate covariance matrix will be specified. Model assumptions will be examined (e.g., QQ plots to assess normally distributed residuals for valid Wald tests). We will make every possible effort to minimize missing data and ensure final assessments for participants opting to discontinue study participation. Missing data, however, is an inevitable problem in a longitudinal study. The mechanism for missingness-missing completely at random (MCAR), missing at random (MAR), nonignorable or not missing at random (NMAR)-will be evaluated prior to implementing methodology intended to minimize bias from missing data.⁽¹¹⁶⁾ We anticipate that ~10% of randomized subjects will not complete the study.

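### Section 10.2's within-period significance screen leaves the covariate list open and permits, without stating, adjustment of the outcome model for variables that KNO3 has changed

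*Combined protocol and SAP*

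**What the plan says.** Section 10.2 sets the analysis out in stages. A paired t-test and a Wilcoxon signed-rank test come first. A linear mixed-effects model follows, "controlling for effects of other covariates such as period, sequence, and a random subject effect nested within sequence".

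Covariates are then chosen by testing: "The intervention groups will initially be compared within each period (time invariant covariates will only be compared for period 1) according to continuous covariates". Categorical covariates are compared within period too, by Fisher's exact test. The consequence is mandatory: "Significant differences between groups on these variables will result in their use as control variables in the modeling of outcome". A second route into the model follows. Each outcome is regressed on intervention, "along with baseline outcome and any other covariates deemed prognostic in preliminary analyses". On the models themselves the section says: "Separate models will be generated for each of the two outcome measures". It first names the co-primary outcomes as peak VO2 and KCCQ.

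The timing of measurements comes from elsewhere:

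- Section 5.4 provides a "washout period during which they will not receive any study medications", and Appendix 1 marks no assessment in the washout column.
- Under Section 4.3.3, only subjects who meet a blood pressure, renal or methemoglobin trigger "will be scheduled for an ad hoc visit for reassessment of values prior to drug initiation in phase 2".
- In Appendix 1, echocardiography, tonometry, laboratory tests and KCCQ are marked at baseline and at the two 4 ± 1 week visits. The expired-gas exercise test is marked only at the two 4 ± 1 week visits.

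**The concern.** The screen compares the two treatments on variables that may have been measured while subjects were taking them. A significant KNO3-versus-KCl difference in such a variable can be a treatment effect rather than an imbalance, so the rule tends to select the variables that KNO3 moves. The trial expects some to move: Specific Aim 3 asks whether KNO3 "reduces late systolic LV load from wave reflections", and Aim 2 concerns LV filling and strain.

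Conditioning on such a variable has two costs. The part of the treatment effect that runs through it is taken out of the estimate. And because it is correlated with treatment, the standard error rises even if it carries none of the effect. Apart from both, a model whose terms depend on significance tests stays open until the data are seen, which matters in a trial of 22 subjects.

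**Working it through.** **1. What the text allows.** The covariates to be screened are said to have been described already, but the only ones named before that point are period, sequence and subject. There is no list and no time point. Restricting time-invariant covariates to period 1 implies that time-varying ones are tested in period 2 as well. If the screen is read as a balance check at entry to each period, period 1 can use baseline values and does no harm. Period 2 has no routine entry measurement, so the latest routine values were taken on the period-1 drug.

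**2. The plan's own power figure.** Inputs from Section 10.1: 22 subjects, 90% retention, two-sided α 0.05, SD of change 1.23 ml/kg/min, detectable effect size 0.66. Completers: 22 × 0.9 = 19.8, taken as 20. A paired t-test (noncentral t, n = 20) at 0.66 gives 79.9%, so the stated 80% is the power of an unadjusted paired test. In ml/kg/min the detectable effect is 0.66 × 1.23 = 0.81. (At the minimum important change, 0.6/1.23 = 0.488, the same formula gives 54.4%. That is a separate matter.)

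**3. Assumptions for the illustration.** None of these is in the documents.

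- One time-varying covariate, shifted by KNO3 by 0.5 between-subject SD.
- Within-subject SD of 0.5 or 1.0 between-subject SDs.
- A quarter of the 0.81 effect runs through it.
- It is selected if a two-sample t-test is significant in either period. Section 10.2 does not say whether one or both are needed.

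The SD of the covariate's paired difference is √2 × 0.5 = 0.707 or √2 × 1.0 = 1.414, so the shift is 0.71 or 0.35 paired SDs. The implied slope is 0.25 × 0.81 / 0.5 = 0.405. The covariate then explains 0.405² × 0.5 / 1.23² = 5%, or 0.405² × 2 / 1.23² = 22%, of the paired outcome variance.

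**4. Direction, by formula.** Regress the KNO3 − KCl outcome difference on an intercept and the covariate difference, which has mean δ and SD s. The intercept then estimates only the unmediated effect, 0.75 × 0.81 = 0.61. With residual variance unchanged, its standard error grows by about √(1 + δ²/s²): √(1 + 0.25/0.5) = 1.22 or √(1 + 0.25/2) = 1.06.

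**5. Size, by simulation.** There were 20,000 AB/BA trials per setting, with 10 + 10 completers and total paired SD held at 1.23. The covariate was added to the period-adjusted regression of within-subject differences only when selected. Results are for within-subject SD 0.5 / 1.0, true effect 0.81:

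| Covariate | Rule | Selected | Mean estimate | Power |
|---|---|---|---|---|
| Not affected by KNO3 | either period | 8% / 9% | 0.81 / 0.81 | 80% / 79% |
| Shift 0.5, none mediated | either period | 31% / 22% | 0.81 / 0.81 | 72% / 76% |
| Shift 0.5, quarter mediated | either period | 31% / 23% | 0.74 / 0.74 | 65% / 71% |
| Shift 0.5 or less | both periods | not tabulated | not tabulated | 79–80% |

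The average estimate stays above 0.61 because the covariate enters in only a minority of trials.

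**6. Baseline term.** No expired-gas test is scheduled at baseline, so a baseline outcome cannot be fitted for peak VO2, or for total work if that is modelled. KCCQ does have a baseline (Section 8.2). In a simulated complete crossover, adding a subject-level baseline left the treatment estimate at 0.2193 and its standard error at 0.2512. This is housekeeping.

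**The case against.** The strongest reply is that the plan never says it will adjust for a mechanistic variable. The summary table in Section 2 lists LV diastolic function, strain and late systolic load among secondary aims and endpoints. Section 10.2 calls the secondary measures outcomes and sends the mechanistic endpoints to their own treatment comparisons and structural equation models. The screen concerns covariates, which is a different word. This stands. A reader might infer that the sponsor plans to adjust for mediators, or that the primary estimate will be biased; the documents support neither. What remains is that the covariate set is undefined, inclusion is mandatory once a test is significant, and no sentence excludes those endpoints or any other on-treatment measure.

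Second, the paired t-test and the Wilcoxon test use no covariates and are untouched. That also stands. But Section 10.2 calls them an initial assessment, follows them with a model it describes as more comprehensive, and does not say which decides.

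Third, the size rests on assumed covariate parameters. A reader might quote much larger losses: a shift of one between-subject SD with half the effect mediated gives power of 23% / 42% under the either-period rule. At within-subject SD 0.5 that shift is 1/0.707 = 1.41 paired SDs, more than twice the 0.66 for which the trial is powered, and nothing in the documents supports it as an expectation.

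**Conclusion.** The point holds as a statement about what the wording permits, and confidence in that is high. Section 10.2 contains a binding, data-driven covariate rule with no restriction to pre-treatment values, in a schedule with no routine pre-treatment measurement for period 2.

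Confidence in the consequence is moderate. It depends on the mixed model being decisive, on an on-treatment variable that KNO3 shifts being screened, and on selection after significance in a single period. Under the stated assumptions the cost is a fall in the average estimate from 0.81 to about 0.74 and in power from about 80% to about 65% / 71%. It is nil for a covariate that KNO3 does not affect, and not visible for shifts of 0.5 or less if both periods must be significant. These figures show direction and plausible scale; they do not forecast this trial's power. The wording should be changed before unblinding, but it does not invalidate the design.

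**What to change.** In Section 10.2:

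- Delete the within-period significance screen, the rule that turns its results into control variables, and the clause admitting covariates judged prognostic on a preliminary look.
- Name as primary, for each endpoint, the mixed model with fixed treatment, period and sequence and a random subject intercept, plus only pre-randomization covariates listed in the SAP before unblinding.
- Label the paired t-test and the Wilcoxon test as supportive.
- State that on-treatment variables are analysed only as outcomes or in the mechanistic analyses already described.
- Drop the baseline-outcome term for peak VO2, and for total work if modelled. This does not change the estimate in complete pairs.

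The cost is SAP wording, with no added visit, subject or procedure. The downside is that a prognostic time-varying covariate that KNO3 does not affect, but that is imbalanced by chance, would no longer be adjusted for. In simulation this gives up about 0 to 2 points of power when the covariate explains 10–50% of the paired variance, because the screen would select it only 8–9% of the time.
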